Official Title: Videos and Simple Text to Empower Parents to Handle Their Sick Children

NCT number: NCT04301206

Date: 5.11.2019

**[name], [name], [name], [name],
[name], [name], [name],
[name].**

***Videos and simple text to empower parents to handle their sick
children***

Date

5.11-2019

Correspondence

[name]

Email: [contact]

Børnelægernes Børnetips, protokol resumé på dansk

Baggrund: I sundhedsvæsenet er der et stigende antal henvendelser fra forældre, der har svært ved at skelne imellem fredelige og alvorlige symptomer hos deres syge børn. Børnelægernes Børnetips er et nyt tiltag, der ønsker at give forældrene en højere grad af viden og mestringsevne (self-efficacy og empowerment), så de ved, hvornår det drejer sig om fredelige symptomer, som de kan hjælpe barnet med hjemme, og hvornår det er alvorlige symptomer, hvor de bør kontakte læge eller Akuttelefonen 1813. I første omgang udarbejdes materiale om de 8 symptomgrupper: 1) opkast og diarre, 2) svært ved at få vejret, 3) feber, 4) ondt i maven, 5) ondt i halsen, 6) et rødt øje, 7) ondt i ørerne, og 8) udslæt, som skønnes at dække omkring 70% af akut sygdom hos børn. Da de fleste symptomer hos syge børn er fredelige, forventes det at projektet kan spare mange familier for at bringe børn til lægeundersøgelse på hospital.

Forældrene foretrækker digital kommunikation og søger sygdomsinformation på internettet, men kvaliteten af den information er varierende. Desuden kan megen sundhedsinformationen fra officielle danske myndigheder fx Sundhedsstyrelsen og Patienthåndbogen, være vanskelig at forstå, ikke mindst når man tilgår det på en smartphone, hvilket forældre ofte gør. Børnelægernes Børnetips tilbyder information på forældrenes smartphones. Materialet er udarbejdet af børnelæger og andre relevante læger, og godkendt af Dansk Pædiatrisk Selskab.

Projekt i samarbejde med Akutberedskabets Akuttelefon 1813: skal afklare om de 8 film gør, at flere forældre svarer, at de ved hvad de skal gøre når deres barn bliver sygt.

Efter opringning til Akuttelefonen 1813 vil forældre til børn i alderen 6 mdr. til 11,9 år blive tilbuddt at deltage. De vil blive informeret om, at de ved deltagelse får tilsendt et link til materialet på deres smartphone, og at de kan se materialet i 72 timer. De vil også få at vide, at ved deltagelse får de næste dag tilsendt et link til et SMS-spørgeskema med 6 korte spørgsmål, samt at deres barns journal igennem de næste 72 timer bliver læst, hvis barnet kommer på hospital. Der vil blive trukket lod om deltagelse. Forældrene der får materialet skal ringe 1813 igen, hvis de ønsker at tale med en sygeplejerske eller læge. Hvis de ikke får tildelt materialet kommer de til at tale med en sygeplejerske eller læge som vanligt.

Forskingsspørgsmålene vil blive besvaret udfri forældres svar på SMS-spørgeskemaet.

Første forskningsspørgsmål: Angav flere forældre, der fik adgang til materialet, høj grad af self-efficacy og empowerment end forældre, der ikke fik adgang til materialet?

Andet forskningsspørgsmål: a) Oplyste forældre, der fik adgang til materialet, i mindre grad, at deres børn var blevet undersøgt af læge end forældre, der ikke fik adgang til materialet, b) Angav forældre, der fik adgang til materialet, hyppigere høj grad af tilfredshed med kontakten til 1813 end forældre, der ikke fik adgang til materialet?

Samtlige projektdata vil blive fuldt anonymiserede, så det ikke på nogen måde er muligt at henføre data til personer. **Sikkerhed ved projektet** bliver undersøgt ved gennemgang af hospitalsjournaler af alle de inkluderede børn indenfor de næste 72 timer efter opkaldet. Ved utilsigtede hændelser vil en sikkerhedskomité tage stilling til om projektet skal afbrydes.

Det forventes, at forskningsspørgsmålene kan besvares indenfor en dataopsamlingsperiode på 3 mdr. Projektet vil ikke forløbe i længere tid end 6 mdr.

Appendix 1 viser hvorledes forældrene vil blive informeret om projektet og hvordan der vil blive indhentet informeret samtykke, samt de 6 SMS-spørgsmål der udsendes dagen efter opkaldet.

Introduction

Is it possible – by using videos and simple action cards about common symptoms in children - to empower parents and citizens to take better care of children with milder symptoms at home and to know when to go to a doctor or hospital? The project will help the parents be empowered so they are more confident about caring for their sick children including to know when it is needed to call for help. Competence in caring for children and safety are important aspects of a good family life.

The project addresses a current challenge in the public health sector since many children are referred to hospitals outside their general practitioners' opening hours, and many of these children exhibit only mild symptoms which require neither treatment nor paraclinical tests, but merely medical parental guidance. The project utilises appropriate means, since most parents value the Internet as an information resource. Thus, the material will meet the users where they are – online on their smartphones.

The nature of the problem: a lot of 'trivial' illness in children

Up to the age of four years, children have from 23 to 80 days of sickness a year, where they couldn't play normally, most days of sickness for children attending day care (1-4). In average the parents reported that the child had had 3.3 episodes of sickness a year and that each period of sickness lasted next to 7 days (4). It may be scaring for parents when their child gets sick, especially when it is for the first time. In about 50% of these contacts, the parents felt the child needed treatment, but in less than 10% of the cases they felt the child was seriously ill (4). Parents with only one child had most medical calls. For children with one or two siblings, doctor's contact was reduced by one third, when compared to first born children, and for children with of three or more siblings' it was reduced to less than one tenth (4). As the average number of children per Danish women is 1.75 only (5), many children are the first-born child.

A Danish study from the Capital Region, in 2013 – the year before the medical helpline 1813 was introduced - found that 28% of the urgent consultations concerned 2.5% of the child population. These children had at least 4 urgent consultations yearly (6). Acute bronchitis was the most frequent diagnosis among these children, which were young (median age of 2.9 years), compared with all the children with an urgent contact (median age of 7.3 years) (6). Moreover, children with young mothers and children with immigrant parents had 37% and 28% increased risk for frequent contact (6), respectively.

A Danish study from the Capital Region, from 2014, the first year of the medical helpline 1813, showed that most calls concerned 0-1-year-old children who seldom exhibited serious conditions (7). The author interpreted the results as if the parents were primarily calling 1813 to get reassurance about the child's condition. When the children got older, the frequency of calls decreased, but in turn, they concerned more serious conditions (7).

Each year there are approximately 190,000 calls to the medical helpline 1813 regarding sick children younger than 12 years (injuries excluded) (8). These children are not so ill that the parents call the emergency helpline 112, but the parents need to contact the health care system outside their general practitioners' opening hours. After contact with the parents, the medical helpline 1813's health professionals may either: 1) refer the child to a paediatric department, 2) refer the

child to assessment in a paediatric urgent care centre (Børnelægevagten), 3) guide the parents to self-care at home, or 4) advised the child to their general practitioners (GP) the next workday.

In 2018, there were 192,000 calls about sick children (injuries excluded) (8). Of these calls, 57% children stayed at home the day the parents called 1813 (31% were guided in self-care and 26% were advised to their GPs the next workday), 40% were referred to the hospital (30% were referred to a paediatric urgent care centre and 10% were referred directly to a paediatric department) and 3% were referred to other options (8).

Many sick children, who are referred to a hospital have mild symptoms which do neither require treatment nor paraclinical tests, but merely parental medical guidance. We estimate it is about 40% of the cases. These consultations can be experienced as unnecessary and inappropriate for the sick child and its parents. Moreover, the visits are expensive for the health system, and the medical staff's attention and time may be directed on the not-so-sick children, so there may be less time for the sicker children referred to a hospital.

A report of the general Danish Emergency Medical Service and the Copenhagen Emergency Service in 2016 showed that children aged 0-4 had the highest number of contacts to the emergency services outside their GPs' opening hours; the number of telephone contacts ranged from 1375 to 1775 per 1000 children. Equivalently, children aged 0-4 years had the highest number of consultations. The number ranged from 475 to 750 per 1000 children, and in Copenhagen it was 500 per 1000 children (9). In Copenhagen 400 per 1000 children aged 0-4 years were referred to the paediatric urgent care centre, like the number in the rest of Denmark (9).

The Internet as a tool to provide an appropriate part of the response to parents' needs

The Internet plays a major role in the daily lives of today's parent, with next to 90% of parent's daily accessing the Internet via their smartphone device (10). It has been reported that parents highly valued the Internet as an information resource in regard to their infant (10-12). They preferred that type of media for information, compared to books and brochures distributed by the hospital from a neonatal intensive care, or a department of Paediatric Surgery (10,11), but a little less than a brochure from a Department of Paediatric otolaryngology (12). However, a high frequency of parents turns to the Internet for medical information (12-15).

There is a concern regarding the quality of the information being available on the Internet (15-16). Reviews conducted in child health related areas, have indicated that quality of health information varies significantly and internet searches may reveal information that is not evidence-based, or may even be inconsistent with international treatment recommendations (16-18). Consequently, there is a need to develop easily accessible evidence-based online information for parents (19).

In Denmark, there is the official homepage <https://www.sundhed.dk/>, which allows every citizen to assess their own health data from the public health services. Moreover, it includes a homepage called 'patient's handbook' <https://www.sundhed.dk/borger/patienthaandbogen/>, which offers information about diseases, symptoms, examinations and treatment and help to self-care. However, it is not an app for a smartphone, it may include too much information, it is based on diagnoses and not symptoms, and it is written which results in difficulties for quite many parents. Moreover, the information is not specific for concerns about sick children. Therefore, the

current 'online guidance' is likely too difficult to handle for parents with an acutely sick child. The Danish Committee for Health Education is a non-profit non-governmental organization with close working relations with public authorities like the Ministry of Health, the National Board of Health and private organizations in the health field. Recently, it has developed three apps: "Pregnant", "Father" and "My baby", but they include limited information and advice regarding sick children.

Is it not easy to create a successful eHealth program for empowerment of parents. In India, a large-scale telemedicine program on childhood diarrhoea and pneumonia was not as successful (20), but in Spain a 2-week online educational program covering major topics in food allergy management was successful for parents with children having food allergy (21).

The World Health Organization (WHO) European Regional Office included empowerment and patient-centered practice as key elements in its Health 2020 report (22), a follow-up on previous WHO study on the effectiveness of empowerment to improve health (23). The earlier WHO research identified empowerment as an essential public health strategy but also called for the ongoing refinement of measures to evaluate empowerment (23). Improved definition of patient empowerment and measures to comprehensively evaluate the concept remain (24,25,26), and this is clearly a need for eHealth science as well (27).

Our new material and workflow

There appears to be a case for helping parents with sick children who often are inexperienced and have little access to advice from family or other parents with more experience. In specific, there seems to be a case for empowering parents with regard to their handling of mildly sick children; a case for more self-efficacy. We want to empower these parents to handle mild and common symptoms in children at home by providing easily understood information. We want to focus on symptoms instead of diagnoses as these are the problems of the children. Moreover, we want to tell the parents about danger signs, so they know when they must contact the medical helpline 1813 or a doctor. This means that we want to empower the parents by increasing their self-efficacy.

Study objective

We will produce 8 videos each lasting about 2.5 minutes, about the following common symptoms: 1) vomiting or diarrhea, 2) difficulties in breathing, 3) fever, 4) abdominal pain, 5) sore throat, 6) a red eye, 7) pain in the ears, and 8) exanthemas. The videos will be accompanied by text, action cards, and be accessible on a smartphone. In the beginning the material will be in Danish only, followed in time by materials also in English and Arabic in order to address the increasing demand for languages other than Danish. The material will be developed in collaboration between paediatricians (medical content) and professional film/app-makers (creative content) and will be approved by the Danish Society of Paediatrics and other relevant scientific societies. We want to study the clinical value of this material before we launch the campaign to the public.

The study objective is to investigate if it is possible by using videos and simple action cards about common symptoms in children - to empower parents and citizens to take better care of sick children with milder symptoms at home including to know when they must call for medical help. The corresponding research question is: Is it possible, by videos and simple action cards about eight common symptoms, to increase the number of parents with high self-efficacy in management of the sick child?

Material and methods

Set up

A prospective randomized controlled trial taking place in the Capital Region of Copenhagen including parents who call the medical helpline 1813 about a sick child aged from 6 months to 11.9 years. Excluded are parents who are not able to speak Danish, who have no Danish telephone number or have no smartphone, children with an injury and those who have participated in the study within the last 72 hours.

The parents who call 1813 will be offered to participate in the study. If they accept, they will be randomized 1:1 to the intervention group (randomized to the new material composed of 8 videos and corresponding smart cards) or to the control group (randomized to current standard care). If the family is randomized to the new material it will be possible to use this material within the next 72 hours after the initial contact to 1813.

The next day in the month at 12 a.m. (at least 12 hours after the call) the participants in the study will receive a text-message with 6 questions, for these questions see Appendix 1. If the parents do not answer the text-message they will get the text-message the following day at 12 a.m.

All case reports of the included children at the hospitals will be reviewed within 3 to 8 days after the call to register the number of children who went to departments of Paediatrics, the diagnosis, if the children had examinations or treatment, if the children were sent home from the hospital or admitted to the departments of Paediatrics, the duration of hospitalization, intensive care admittance and mortality within 72 hours after the initial call.

At the Copenhagen Emergency Services the included patients in the study will be identified, and it will be noted the number and the time of further contacts to the medical helpline within the next 72 hours, and if the child was referred to hospital.

Moreover, for every included parent and child (family) it will be noted the number and time the family used the new material, and which kind of the material was used and for how long time.

To investigate if bias was present in the study we want to study: age, sex, if the patients were referred to hospital, admitted to hospital, the duration of hospitalization, intensive care admittance and mortality within 72 hours after the initial call. We also want to study: age, sex, if the patients were referred to hospital for the patients who accepted to participate in the study versus those who did not accept to participate.

Aim of the study

Did the new material about sick children result in high parental self-efficacy among the parents who were allowed to watch the material?

Did new material about sick children result in less children examined by a doctor and more satisfied parents?

Primary outcome

Data of the electronic questionnaire from the parents;

High parental self-efficacy defined as parents who answered "i meget høj grad" or "i høj grad" to at least two of the three questions:

"Hvor godt kunne du passe dit syge barn hjemme, efter du søgte hjælp ved at ringe 1813?",
"Ved du hvad du kan gøre hjemme, hvis dit barn får samme symptomer en anden gang? and
"Ved du, hvornår det er så alvorligt, at du skal kontakte læge eller 1813, hvis dit barn får samme
symptomer en anden gang?"

Secondary outcomes

Data of the electronic questionnaire from the parents;

- Use of professional consultations: Yes to the question "Har en læge/sygeplejerske undersøgt dit barn under dette sygdomsforløb?" (både egen læge og læge på hospital).
- Satisfied with the contact to the acute telephone 1813: Yes (svar "i meget høj grad" og "i høj grad") to the question "Er du overordnet tilfreds med den hjælp du fik, da du kontaktede 1813?"

Exploratory outcomes

Data of the electronic questionnaire from the parents;

- The medical status of the sick child "Hvordan har dit barn det nu, sammenholdt med da du kontaktede 1813?"

Data from the Copenhagen Emergency Services;

- The number of telephone contacts to 1813, the age and the sex of the child.
- The number of parents who called 1813 within the next 72 hours after the initial call.
- The number of patients, who were referred to a hospital within the next 72 hours after the initial call.

Data of the calls from the videos and action cards;

- The number of times the 8 videos and the eight action cards were used within the next 72 hours after initial contact to 1813.
- The duration and types of videos and action cards the parents watched within the next 72 hours.

Data from the case reports from Epic (Sundhedsplatformen);

- The number of patients, who went to a hospital within the next 72 hours after the initial contact to 1813, and the time of arrival.
- The number and diagnoses of patients who did neither get treatment nor paraclinical tests, but merely parental medical at hospital.
- The number and diagnoses of patients who went home from the hospital with treatment for example antibiotics or painkillers.
- The number of number and diagnoses of sick children who were inpatients in less than 12 hours, more than 12 hours, more than 24 hours in the following 72 hours or went to the intensive care unit.

Automatic speak when the parents call 1813 and the SMS-questions the next day

Please notice **Appendix 1**, in Danish, for specific information.

Safety measures: The paediatric departments in the Capital Region will be made aware of the study. The case reports of the included children at the hospitals will be reviewed within 3 to 8 days after the call. This will primarily be done by the ph.d. student doctor, who is blinded for the information of the study group (intervention versus control group). We will register the number of children who went to departments of Paediatrics, the diagnosis, the duration of hospitalization, intensive care admittance and mortality within 72 hours after the call. It will also be noted, if there are cases of unexpected serious adverse events, near-misses, death, and if it looked as if the child went to hospital later than optimal based on parental delay. In these cases, this information will be presented for a **Data Safety Committee** and it will be revealed if the child was randomized to the intervention or to the control group. The **Data Safety Committee** will advise the study group on continuation, modification, or stopping the trial.

Sample size

We want to be able to detect if the intervention with videos and action cards increases the proportions of parents who expressed high self-efficacy by 5%. We do not know this actual proportion. If it is actual 50%, we want to detect an increase to 55%. We want a p-value of 0.05 and a probability (power) of 80%.

It will require data from about 3300 text-messages (SMSs) in total, randomized in two equal groups (<http://www.openepi.com/SampleSize/SSCohort.htm>).

If the baseline is at a higher level, for example 70% then we want an to be able to detect an increase to 75%, and with the same p-value and power we then require totally 2520 SMSs.

There are about 160.000 calls concern children of at least 6 months of age to the medical helpline 1813 (18).

If we suggest that 25% of the parents to the sick children agree to be randomized, and that 40% of the included parents answers the text-message the next day, then we can include $(160,000 \times 0.25)/365 =$ about 110 children a day, and we will get about 44 text-messages a day. Then we need $2520/44 - 3300/44 = 57- 75$ days to include enough patients. It is less than 3 months.

In the data from the Copenhagen Emergency Services, and data from the safety measures we will not have loss to follow up, since data from the Copenhagen Emergency Medical Services and from all four Departments of Paediatrics in the Capital Region are collected routinely.

In the data of the calls from the cases we also suggest that all contacts are safety stored so we will have no loss to follow-up.

We suggest we have data to answer our research question within 3 months, and the study will be stopped after 6 months.

Stop of the study before an answer our research question

In cases of serious adverse events the study group will consider stopping the study. This will also be the case if the satisfaction with the contact to the acute telephone 1813 drops to a very low level.

Statistics

The primary analysis will use Chi-square and a two-sided level of significance of $p < 0.05$ for the primary outcome and a $p < 0.025$ for the two secondary outcomes. All other outcomes are exploratory and the statistical methods will be adapted as appropriate. The results from these exploratory analyses will not be used to claim clinical efficacy but used to design new studies. This is an important aspect since new studies can be rapidly designed and performed once the project set-up is in place.

The dataset will be rich and allow exploration of the effect of individual videos, as well as subgroup analyses.

We believe that our set up is robust, as the sick children are included based on electronic equipment, not adding extra work on the medical personnel, the operators. The follow up to the parents by text message the next day is also based on electronic equipment and the follow-up in the medical case reports after 72 hours, for safety reasons, is based on easily available information, if we have the relevant permits for this.

Ethics and transparency

The parents are informed about the study by an automatic voice in the phone and if they press 1, the value for accept, it is taken as their informed consent. The project will be described in short, like this protocol resumé in Danish, at the webpage of the Copenhagen Emergency Service, and it will be possible to link to the study at <https://clinicaltrials.gov/>.

The telephone call will be recorded in the Emergency Medical Services system, based on the actual regular routine. Before initiating the study, the protocol will be submitted to the ethics committee of the Capital Region in Denmark, which may consider it outside their mandate. In this case the project will be submitted to "Videncenter for dataanmeldelse, Rigshospitalet".

In the project the data will be completely anonymized and it is in no way possible to link data with actual people.

The study will be registered at <https://clinicaltrials.gov/> before enrolment of the first patient.

After the first 400 SMS-answers, we will perform an interim analysis to study the frequency of acceptance, and the frequency of high self-efficacy, as well as how the videos have worked technically. Moreover, we will study if the number of SMS-answers from the two groups of families, those randomized to intervention and those randomized to control, are about the same size.

After the first 1000 SMS-answers, we will also make an interim analysis to study the effect of the videos and the action cards. This will also include an examination of a significant difference is exhibited between the number of children staying at home the day the parents call 1813 after having the possibility to watch the videos and read the action cards.

Collaborators

The project will be done in cooperation between the project group of "Børnelægernes Børnetips", the Copenhagen Emergency Medical Services, the Headquarter at the Capital Region of Denmark and the Faculty of Health and Medical Sciences, University of Copenhagen, Denmark.

The group “Børnelægernes Børnetips” consists of about 15 doctors who are paediatricians or coming-up paediatricians who cooperate with “Children’s Life - see my heart! (Børneliv – se mit hjerte!). A non-profit medical organization run by young doctors www.boerneliv.org, which has experience in doing videos of sick children and in teach children and their teachers in how the body works and emergency help.

Project applicants

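### The check for selection into the trial compares hospital referral in decliners with both randomised arms combined, so half of any effect of allocation on referral enters it

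*Combined protocol and SAP*

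**What the plan says.** The protocol, Material and methods, Set up, describes two checks.

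- **A general bias check.** It begins "To investigate if bias was present in the study we want to study: age, sex, if the patients were referred to hospital" and goes on to admission, length of stay, intensive care and mortality within 72 hours. No comparison groups are named.
- **A participation check.** Age, sex and referral are compared "for the patients who accepted to participate in the study versus those who did not accept to participate". No split by arm is mentioned.

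The same section puts acceptance before allocation: "If they accept, they will be randomized 1:1 to the intervention group". Those who accepted are therefore both arms together.

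Referral is also a trial outcome. Exploratory outcomes lists "The number of patients, who were referred to a hospital within the next 72 hours after the initial call", and a further item there, on hospital stays, reads in part "inpatients in less than 12 hours, more than 12 hours, more than 24 hours in the following 72 hours or went to the intensive care". Reduced use of doctors and hospitals is an aim: the Danish summary says "forventes det at projektet kan spare mange familier for at bringe børn til lægeundersøgelse på hospital", and Aim of the study asks "Did new material about sick children result in less children examined by a doctor and more satisfied parents". The Danish summary also says that parents given the material must ring 1813 again if they want to speak to a nurse or doctor, whereas controls speak to one as usual.

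**The concern.** A participation check asks whether those who joined differ from those who did not. It needs a variable that joining has not itself altered. Age and sex qualify. Referral within 72 hours does not qualify for the intervention half of the accepters: their route to a professional differs from usual care from the moment of allocation, and the material is intended to reduce hospital visits. Decliners and controls both follow the usual route.

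If allocation lowers referral, the combined accepters will look less often referred than decliners even when the two groups were alike at the time of the call. That could be taken to mean that milder cases were enrolled. Conversely, real selection of more severe cases could be cancelled out and missed.

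Representativeness matters here. The plan expects 25% of parents to accept and 40% of those to answer the text message, so about 0.25 × 0.40 = 10% of callers supply the primary outcome. Referral is the only variable in the participation check that bears on severity.

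**Working it through.** **The plan's own figures (Sample size).** Neither check has a stated figure of its own, so the plan's totals serve only to set group sizes.

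- Accrual: 160,000 × 0.25 / 365 = 109.6, about 110 accepters a day; × 0.40 = 43.8, about 44 answers a day; 2520/44 = 57 days and 3300/44 = 75 days. These agree with the plan.
- Required answers, two-sided 0.05, 80% power: 50% v 55% gives 3130 without and 3210 with continuity correction (plan: about 3300). 70% v 75% gives 2502 and 2582 (plan: 2520). The corrected formula is within 3% of both.

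**Group sizes for the illustration.**

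- Upper end: 3300/0.40 = 8,250 accepters (also 110 × 75). With 25% acceptance, non-accepters = 3 × 8,250 = 24,750.
- Lower end: 2520/0.40 = 6,300 accepters and 18,900 non-accepters.

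**Assumptions.** There is no selection. Referral is 40% in decliners and controls (the 2018 figure in the background section). The effect *d* on referral is varied because the documents give none.

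**Formula.** Combined accepter rate = (0.40 + 0.40 − *d*)/2 = 0.40 − *d*/2, so the spurious difference is *d*/2.

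For *d* = 10 points at the upper end, SE = √(0.35 × 0.65/8,250 + 0.40 × 0.60/24,750) = 0.0061 and z = 0.050/0.0061 = 8.2. A pooled variance gives 8.1.

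| Assumed effect *d* | Combined accepters | Spurious difference | z, 8,250 v 24,750 | Chance of p<0.05, lower to upper end |
|---|---|---|---|---|
| 2 points | 39.0% | 1.0 | – | 29% to 36% |
| 3 points | 38.5% | 1.5 | 2.4 | 56% to 68% |
| 5 points | 37.5% | 2.5 | 4.0 | 94% to 98% |
| 10 points | 35.0% | 5.0 | 8.1 to 8.2 | about 100% |

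Without the artefact the last column would be 5%.

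**Masking.** Suppose accepters would be referred 5 points more often under usual care (45%) and allocation lowers referral by 10 points (35%). The combined rate is (45 + 35)/2 = 40%, equal to decliners, and the selection is invisible.

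**Control-arm accepters only.** With no selection the expected difference is zero whatever *d* is. At the upper end there are 8,250/2 = 4,125 controls: SE = √(0.24 × (1/4,125 + 1/24,750)) = 0.0082, and the difference detectable with 80% power is 2.80 × 0.0082 = 2.3 points. At the lower end (3,150 v 18,900) it is 2.80 × 0.0094 = 2.6 points.

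**The general bias check.** The text allows two readings.

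- *Between arms:* only age and sex on the list precede randomisation. A difference in the rest is an effect of allocation or chance and does not diagnose bias.
- *Text-message repliers versus non-repliers:* the hospital variables are useful, because Sample size says these data have no loss to follow-up. If reply rates differ by arm, however, combining the arms mixes an arm effect into the comparison. Working within each arm avoids this.

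**The case against.** A reader might infer that both checks would turn a working intervention into apparent bias. The documents do not support that for the longer list. No comparison groups are named, and repliers versus non-repliers is at least as plausible a reading as arm versus arm. On that reading, a false signal from combining the arms would also require reply rates to differ between arms. What can be said of that check is that its groups are missing.

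A reader might also infer that every listed variable is something the material is meant to change. That fits referral and hospital attendance. Intensive care and mortality appear under Safety measures; they are measured after randomisation, but nothing presents them as targets.

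Neither check carries a test, threshold or decision rule, so the z values put a formal test on what may be a purely descriptive table. Referral is also an exploratory outcome; if it is reported by arm, a careful reader could see what drives the combined figure. The control-only comparison could even be made afterwards from the same data.

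The inputs are approximate. The 40% covers all 2018 calls about sick children, including infants below the trial's age limit, and some non-accepters may be ineligible callers rather than decliners.

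All of this stands, and it limits the size of the point. It does not remove it: the participation check, as written, compares referral in a group that is half treated with a group that is wholly untreated.

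**Conclusion.** The point holds for referral in the participation check. Half of any effect of allocation on referral is mixed into it, so it can show selection that is not there or hide selection that is. The shifts of 1.5, 2.5 and 5.0 points are illustrations resting on assumed effects of 3, 5 and 10 points, 40% referral in decliners and controls, the upper end of the plan's 57 to 75 days, and all non-accepters counted as eligible decliners. That accepters are combined is the plain reading of the sentence; the protocol does not use the word.

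For the general bias check, the supportable finding is that the comparison groups need to be stated.

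It would be wrong to conclude that the trial's results are biased. The primary and secondary analyses, the sample size and the safety review do not depend on either check, and age and sex remain valid in both. This is a minor point about interpreting selection and generalisability.

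**What to change.** Reword the one paragraph under Set up:

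1. **Participation check.** Compare referral between decliners and control-arm accepters only. Keep all accepters for age and sex.
2. **General bias check.** State the groups. If it is between arms, use only pre-randomisation variables such as age and sex, and report referral, admission, stay, intensive care and mortality as outcomes. If it is text-message repliers versus non-repliers, keep the full list and make the comparison within each arm.

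No new data are needed. The cost is half the accepters in the single comparison of referral, which would still detect a difference of about 2.3 points (2.6 at the lower end of accrual) with 80% power.
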